6. STATISTICAL CONSIDERATIONS AND ANALYSIS PLAN

Because of the non-comparative nature of the study, no statistical tests are planned. All efficacy parameters will be summarized descriptively. Demographic and baseline characteristics will be summarized descriptively.

6.1 DETERMINATION OF SAMPLE SIZE

No formal sample size calculations were performed for this OLE study. The maximum number of patients eligible for enrollment is approximately 580 (i.e., all patients enrolled in Study GA29350).

6.2 SUMMARIES OF CONDUCT OF STUDY

The number of patients who enroll, discontinue, or complete the study will be summarized. Reasons for premature study withdrawal will be listed and summarized. Enrollment and major protocol deviations will be listed and evaluated for their potential effects on the interpretation of study results.

6.3 SUMMARIES OF DEMOGRAPHIC AND BASELINE CHARACTERISTICS

Demographic and baseline characteristics such as age, sex, weight, and disease activity will be summarized using means or medians for continuous variables and proportions for categorical variables. Medical history including diagnoses and treatment will be tabulated.

6.4 SAFETY ANALYSES

The safety analyses will include all patients who received at least one dose of study drug, during this OLE study. Safety will be analyzed on the basis of reported/documented adverse events, laboratory results, and vital signs, including adverse events of special interest, separated by treatment cohorts during the blinded study (GA29350).

6.5 EFFICACY ANALYSES

Patient efficacy data will be summarized separated by treatment cohorts during the blinded study (GA29350). Efficacy summary will be based on the intent-to-treat population, defined as all eligible patients enrolled into this OLE study. Analyses of additional study populations (e.g., completers, and per protocol [excluding major protocol violators]) will be performed as supportive evaluations. Additional subgroup analyses may be conducted on an exploratory basis. Details will be provided in the Data Analysis Plan.

6.6 PHARMACOKINETIC ANALYSES

Systemic GDC-0853 exposures will be evaluated using a population PK approach, and estimates of PK parameters (including total exposure [AUC] and clearance following oral dosing) will be generated and summarized by PK parameter (mean, SD, coefficient of variation, median, minimum, and maximum). The extent of interpatient variability will be evaluated, and potential sources of variability will be assessed. Relationships between exposures, biomarkers, and efficacy endpoints will be characterized.

Additional PK analyses will be conducted during and/or at the end of the study as appropriate.

6.7 BIOMARKER ANALYSES

PD biomarker analyses will include patients with at least one predose and post-dose biomarker assessment. Descriptive statistics in PD biomarkers will be listed by dose, cohort, and response status. Data will be analyzed by absolute levels of the biomarker as well as normalized to baseline levels. Additional PD analyses will be conducted as appropriate. The ability of biomarkers (e.g., but not limited to CXCL13 and sICAM1) measured at baseline to identify a subset of patients with enhanced clinical benefit to GDC-0853 will also be evaluated.

6.8 INTERIM ANALYSIS

No formal interim analysis is planned. Data cuts may be performed at appropriate time points for inclusion in the submission with the main studies to support the safety profile.

7. DATA COLLECTION AND MANAGEMENT

7.1 DATA QUALITY ASSURANCE

The Sponsor will be responsible for data management of this study, including quality checking of the data. Data entered manually will be collected via EDC through use of eCRFs. Sites will be responsible for data entry into the EDC system. In the event of discrepant data, the Sponsor will request data clarification from the sites, which the sites will resolve electronically in the EDC system.

The Sponsor will produce an EDC Study Specification document that describes the quality checking to be performed on the data. Central laboratory data and other additional non-eCRF data will be sent directly to the Sponsor, using the Sponsor's standard procedures to handle and process the electronic transfer of these data.

eCRFs and correction documentation will be maintained in the EDC system's audit trail. System backups for data stored by the Sponsor and records retention for the study data will be consistent with the Sponsor's standard procedures.

PRO data will be collected through the use of an electronic device provided by a vendor. The device is designed for entry of data in a way that is attributable, secure, and

accurate, in compliance with U.S. Food and Drug Administration (FDA) regulations for electronic records (21 CFR Part 11). The electronic data are available for view access only via secure access to a web server. Only identified and trained users may view the data, and their actions become part of the audit trail. The Sponsor will have view access only. System backups for data stored by the Sponsor and records retention for the study data will be consistent with the Sponsor's standard procedures.

7.2 ELECTRONIC CASE REPORT FORMS

eCRFs are to be completed through use of a Sponsor-designated EDC system. Sites will receive training and have access to a manual for appropriate eCRF completion. eCRFs will be submitted electronically to the Sponsor and should be handled in accordance with instructions from the Sponsor.

All eCRFs should be completed by designated, trained site staff. eCRFs should be reviewed and electronically signed and dated by the investigator or a designee.

At the end of the study, the investigator will receive patient data for his or her site in a readable format on a compact disc that must be kept with the study records. Acknowledgement of receipt of the compact disc is required.

7.3 ELECTRONIC PATIENT REPORTED OUTCOME

Patients will use an electronic device to capture PRO data. The data will be transmitted wirelessly automatically after entry to a centralized database maintained by the electronic device vendor.

Once the study is complete, the data, audit trail, and trial and system documentation will be archived. The investigator will receive patient data for the site in both human- and machine-readable formats on an archival-quality compact disc that must be kept with the study records as source data. Acknowledgement of receipt of the compact disc is required. In addition, the Sponsor will receive all data in a machine-readable format on a compact disc.

7.4 SOURCE DATA DOCUMENTATION

Study monitors will perform ongoing source data verification to confirm that critical protocol data (i.e., source data) entered into the eCRFs by authorized site personnel are accurate, complete, and verifiable from source documents.

Source documents (paper or electronic) are those in which patient data are recorded and documented for the first time. They include but are not limited to hospital records, clinical and office charts, laboratory notes, memoranda, patient-reported outcomes, ClinROs, evaluation checklists, pharmacy dispensing records, recorded data from automated instruments, copies of transcriptions that are certified after verification as being accurate and complete, microfiche, photographic negatives, microfilm or magnetic

media, X-rays, patient files, and records kept at pharmacies, laboratories, and medico-technical departments involved in a clinical trial.

Before study initiation, the types of source documents that are to be generated will be clearly defined in the Trial Monitoring Plan. This includes any protocol data to be entered directly into the eCRFs (i.e., no prior written or electronic record of the data) and considered source data.

Source documents that are required to verify the validity and completeness of data entered into the eCRFs must not be obliterated or destroyed and must be retained per the policy for retention of records described in Section 7.6.

To facilitate source data verification, the investigators and institutions must provide the Sponsor direct access to applicable source documents and reports for trial-related monitoring, Sponsor audits, and IRB/EC review. The study site must also allow inspection by applicable health authorities.

7.5 USE OF COMPUTERIZED SYSTEMS

When clinical observations are entered directly into a study site's computerized medical record system (i.e., in lieu of original hardcopy records), the electronic record can serve as the source document if the system has been validated in accordance with health authority requirements pertaining to computerized systems used in clinical research. An acceptable computerized data collection system allows preservation of the original entry of data. If original data are modified, the system should maintain a viewable audit trail that shows the original data as well as the reason for the change, name of the person making the change, and date of the change.

7.6 RETENTION OF RECORDS

Records and documents pertaining to the conduct of this study and the distribution of IMP, including eCRFs, electronic PRO data (if applicable), Informed Consent Forms, laboratory test results, and medication inventory records, must be retained by the Principal Investigator for at least 15 years after completion or discontinuation of the study, or for the length of time required by relevant national or local health authorities, whichever is longer. After that period of time, the documents may be destroyed, subject to local regulations.

No records may be disposed of without the written approval of the Sponsor. Written notification should be provided to the Sponsor prior to transferring any records to another party or moving them to another location.

8. ETHICAL CONSIDERATIONS

8.1 COMPLIANCE WITH LAWS AND REGULATIONS

This study will be conducted in full conformance with the ICH E6 guideline for Good Clinical Practice and the principles of the Declaration of Helsinki or the laws and regulations of the country in which the research is conducted, whichever affords the greater protection to the individual. The study will comply with the requirements of the ICH E2A guideline (Clinical Safety Data Management: Definitions and Standards for Expedited Reporting). Studies conducted in the United States or under a U.S. Investigational New Drug (IND) application will comply with U.S. FDA regulations and applicable local, state, and federal laws. Studies conducted in the European Union or European Economic Area will comply with the E.U. Clinical Trial Directive (2001/20/EC).

8.2 INFORMED CONSENT

The Sponsor's sample Informed Consent Form (and ancillary sample Informed Consent Forms such as a Child's Informed Assent Form or Home Nursing Informed Consent Form, if applicable) will be provided to each site. If applicable, it will be provided in a certified translation of the local language. The Sponsor or its designee must review and approve any proposed deviations from the Sponsor's sample Informed Consent Forms or any alternate consent forms proposed by the site (collectively, the "Consent Forms") before IRB/EC submission. The final IRB/EC—approved Consent Forms must be provided to the Sponsor for health authority submission purposes according to local requirements.

If applicable, the Informed Consent Form will contain separate sections for any optional procedures. The investigator or authorized designee will explain to each patient the objectives, methods, and potential risks associated with each optional procedure. Patients will be told that they are free to refuse to participate and may withdraw their consent at any time for any reason. A separate, specific signature will be required to document a patient's agreement to participate in optional procedures. Patients who decline to participate will not provide a separate signature.

The Consent Forms must be signed and dated by the patient or the patient's legally authorized representative before his or her participation in the study. The case history or clinical records for each patient shall document the informed consent process and that written informed consent was obtained prior to participation in the study.

The Consent Forms should be revised whenever there are changes to study procedures or when new information becomes available that may affect the willingness of the patient to participate. The final revised IRB/EC-approved Consent Forms must be provided to the Sponsor for health authority submission purposes.

Patients must be re-consented to the most current version of the Consent Forms (or to a significant new information/findings addendum in accordance with applicable laws and

IRB/EC policy) during their participation in the study. For any updated or revised Consent Forms, the case history or clinical records for each patient shall document the informed consent process and that written informed consent was obtained using the updated/revised Consent Forms for continued participation in the study.

A copy of each signed Consent Form must be provided to the patient or the patient's legally authorized representative. All signed and dated Consent Forms must remain in each patient's study file or in the site file and must be available for verification by study monitors at any time.

For sites in the United States, each Consent Form may also include patient authorization to allow use and disclosure of personal health information in compliance with the U.S. Health Insurance Portability and Accountability Act (HIPAA) of 1996. If the site utilizes a separate Authorization Form for patient authorization for use and disclosure of personal health information under the HIPAA regulations, the review, approval, and other processes outlined above apply except that IRB review and approval may not be required per study site policies.

8.3 INSTITUTIONAL REVIEW BOARD OR ETHICS COMMITTEE

This protocol, the Informed Consent Forms, any information to be given to the patient, and relevant supporting information must be submitted to the IRB/EC by the Principal Investigator and reviewed and approved by the IRB/EC before the study is initiated. In addition, any patient recruitment materials must be approved by the IRB/EC.

The Principal Investigator is responsible for providing written summaries of the status of the study to the IRB/EC annually or more frequently in accordance with the requirements, policies, and procedures established by the IRB/EC. Investigators are also responsible for promptly informing the IRB/EC of any protocol amendments (see Section 9.6).

In addition to the requirements for reporting all adverse events to the Sponsor, investigators must comply with requirements for reporting serious adverse events to the local health authority and IRB/EC. Investigators may receive written IND safety reports or other safety-related communications from the Sponsor. Investigators are responsible for ensuring that such reports are reviewed and processed in accordance with health authority requirements and the policies and procedures established by their IRB/EC, and archived in the site's study file.

8.4 CONFIDENTIALITY

The Sponsor maintains confidentiality standards by coding each patient enrolled in the study through assignment of a unique patient identification number. This means that patient names are not included in data sets that are transmitted to any Sponsor location.

Patient medical information obtained by this study is confidential and may be disclosed to third parties only as permitted by the Informed Consent Form (or separate

authorization for use and disclosure of personal health information) signed by the patient, unless permitted or required by law.

Medical information may be given to a patient's personal physician or other appropriate medical personnel responsible for the patient's welfare, for treatment purposes.

Data generated by this study must be available for inspection upon request by representatives of national and local health authorities, Sponsor monitors, representatives, and collaborators, and the IRB/EC for each study site, as appropriate.

8.5 FINANCIAL DISCLOSURE

Investigators will provide the Sponsor with sufficient, accurate financial information in accordance with local regulations to allow the Sponsor to submit complete and accurate financial certification or disclosure statements to the appropriate health authorities. Investigators are responsible for providing information on financial interests during the course of the study and for 1 year after completion of the study (i.e., LPLV).

9. STUDY DOCUMENTATION, MONITORING, AND ADMINISTRATION

9.1 STUDY DOCUMENTATION

The investigator must maintain adequate and accurate records to enable the conduct of the study to be fully documented, including but not limited to the protocol, protocol amendments, Informed Consent Forms, and documentation of IRB/EC and governmental approval. In addition, at the end of the study, the investigator will receive the patient data, including an audit trail containing a complete record of all changes to data.

9.2 PROTOCOL DEVIATIONS

The investigator should document and explain any protocol deviations. The investigator should promptly report any deviations that might have an impact on patient safety and data integrity to the Sponsor and to the IRB/EC in accordance with established IRB/EC policies and procedures.

9.3 SITE INSPECTIONS

Site visits will be conducted by the Sponsor or an authorized representative for inspection of study data, patients' medical records, and eCRFs. The investigator will permit national and local health authorities, Sponsor monitors, representatives, and collaborators, and the IRBs/ECs to inspect facilities and records relevant to this study.

9.4 ADMINISTRATIVE STRUCTURE

The study will be conducted globally. The contract research organization will be responsible for submission to IRB/ECs for approval of the study protocol, patient recruitment, study conduct, data collection, and reporting.

9.5 PUBLICATION OF DATA AND PROTECTION OF TRADE SECRETS

Regardless of the outcome of a trial, the Sponsor is dedicated to openly providing information on the trial to healthcare professionals and to the public, both at scientific congresses and in peer-reviewed journals. The Sponsor will comply with all requirements for publication of study results. For more information, refer to the Roche Global Policy on Sharing of Clinical Trials Data at the following Web site:

http://www.rochetrials.com/pdf/RocheGlobalDataSharingPolicy.pdf

The results of this study may be published or presented at scientific congresses. For all clinical trials in patients involving an IMP for which a marketing authorization application has been filed or approved in any country, the Sponsor aims to submit a journal manuscript reporting primary clinical trial results within 6 months after the availability of the respective clinical study report. In addition, for all clinical trials in patients involving an IMP for which a marketing authorization application has been filed or approved in any country, the Sponsor aims to publish results from analyses of additional endpoints and exploratory data that are clinically meaningful and statistically sound.

The investigator must agree to submit all manuscripts or abstracts to the Sponsor prior to submission for publication or presentation. This allows the Sponsor to protect proprietary information and to provide comments based on information from other studies that may not yet be available to the investigator.

In accordance with standard editorial and ethical practice, the Sponsor will generally support publication of multicenter trials only in their entirety and not as individual center data. In this case, a coordinating investigator will be designated by mutual agreement.

Authorship will be determined by mutual agreement and in line with International Committee of Medical Journal Editors authorship requirements. Any formal publication of the study in which contribution of Sponsor personnel exceeded that of conventional monitoring will be considered as a joint publication by the investigator and the appropriate Sponsor personnel.

Any inventions and resulting patents, improvements, and/or know-how originating from the use of data from this study will become and remain the exclusive and unburdened property of the Sponsor, except where agreed otherwise.

Appendix 1 Schedule of Assessments

							Treat	ment V	isits								
Week	0 ^a	4	8	12	16 ^b	20 ^b	24	28 ^b	32 ^b	36	40 ^b	44 ^b	48 ^b	52	SC/		
Day (±days)	1 °	28 (±4)	56 (±4)	84 (±4)	112 (±3)	140 (±3)	168 (±7)	196 (±7)	224 (±7)	252 (±7)	280 (±7)	308 (±7)	336 (±7)	365 (±7)	SFU ^d (±7)	ET	UV e
Informed consent ^f	Х																
General medical history and baseline conditions	Х																
Inclusion/exclusion criteria	Х																
Concomitant medications	x ^g	Х	Х	х			Х			Х				Х	х	Х	Х
Adverse events	x ^g	Х	Х	х			Х			Х				Х	х	Х	Х
Vital signs ^h	x ^g	Х	Х	х			Х			Х				Х	х	Х	Х
Weight	x ^g														х	Х	
Complete physical examination i	x ^g																
Limited physical examination ^j		Х	Х	х			Х			Х				Х	х	Х	Х
ECG ^k	x ^g	Х	Х	х			Х			Х				Х	х	Х	Х
GDC-0853 administration in clinic	X m	Х	Х	х													
Hematology ⁿ	x ^g	Х	Х	х			Х			Х				Х	х		Х
Chemistry °	x ^g	Х	Х	х			Х			Х				Х	х		Х
Coagulation studies PT/PTT																	Х
Pregnancy test (urine) women ^p	x ^g	Х	Х	х	Х	Х	Х	Х	Х	Х	Х	Х	Х	Х	х	Х	Х
Drug dispensing	х	х	х	х	х	х	x	х	х	х	x	х	x				
Urinalysis ^q	х ^g	Х	Х	Х			Х			Х				Х	Х	Х	Х
Quantitative Ig ^r	x ^g			Х			Х			Х				Х			Х
Lipid panel ^s				Х											Х	Х	
Rheumatoid Factor/anti-CCP				х											х		

GDC-0853—Genentech, Inc. 109/Protocol GA30067, Version 2

Appendix 1 Schedule of Assessments (cont.)

		Treatment Visits															
Week	0 ^a	4	8	12	16 ^b	20 b	24	28 ^b	32 ^b	36	40 ^b	44 ^b	48 ^b	52	SC/		
Day (±days)	1 °	28 (±4)	56 (±4)	84 (±4)	112 (±3)	140 (±3)	168 (±7)	196 (±7)	224 (±7)	252 (±7)	280 (±7)	308 (±7)	336 (±7)	365 (±7)	SFU ^d (±7)	ET	UV ^e
TBNK	x ^g			х			Х							Х	х	Х	Х
ACR/DAS:																	
CRP	x ^g	Х	х	х			Х			Х				Χ	х	Х	Х
ESR (on site or at local laboratory)	x ^g	х	х	х			х			х				х	х	Х	х
Tender/painful joint count (68), swollen joint count (66)	x ^g	х	х	X t			X ^t			х				х	х	х	х
Patient's Assessment of Arthritis Pain (VAS) ^u	x ^g	х	х	х			Х			х				х	х	х	х
Patient Global Assessment of Arthritis (VAS) ^u	x ^g	х	х	х			Х			х				х	х	х	х
Physician's Global Assessment of Arthritis (VAS) ^v	x ^g	х	х	х			Х			х				х	х	х	х
HAQ-DI ^u	x ^g	х	х	Х			х			х				Х	Х	х	х
SF-36v2 ^u	x ^g			Х			Х							Х	Х		
FACIT-Fatigue Scale ^u	x ^g			Х			Х							Х	Х		
Blood for PK assessment ×	x ^g			Х										Х		Х	х
PBMC protein lysate ^u (U.S. sites only)	x ^g			х										х	х		
Blood for FACS (U.S. sites only) w	x ^g			Х										Х	x		
Serum biomarkers	X ^g , x			x ^x										Х	х		
Plasma biomarkers	x ^g , x			X x			-		_					Х	x		

GDC-0853—Genentech, Inc. 110/Protocol GA30067, Version 2

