4.5 PATIENT, TREATMENT, STUDY, AND SITE DISCONTINUATION

4.5.1 Patient Discontinuation

Patients have the right to voluntarily withdraw from the study at any time for any reason. In addition, the investigator has the right to withdraw a patient from the study at any time. Reasons for withdrawal from the study may include but are not limited to the following:

- Patient withdrawal of consent at any time
- Any medical condition that the investigator or Sponsor determines may jeopardize
 the patient's safety if he or she continues in the study
- Investigator or Sponsor determines it is in the best interest of the patient
- Patient non-compliance, as per Principal Investigator's discretion

Every effort should be made to obtain information on patients who withdraw from the study. The primary reason for withdrawal from the study should be documented on the appropriate eCRF. However, patients will not be followed for any reason after consent has been withdrawn. Patients who withdraw from the study will not be replaced.

If a patient discontinues the study prior to the Week 52 treatment completion visit, an early termination visit should be conducted. These patients should return for the 8-week safety follow-up visit in this study (see Appendix 1).

Patients who discontinue the study during the safety follow-up period but prior to completion of the 8-week safety follow-up will be asked to return to the clinic within 30 days (± 7 days) after the last dose of study drug or last scheduled visit for an early termination visit (see Appendix 1).

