4.5.2 Study Treatment Discontinuation

Patients must discontinue study treatment if they experience any of the following:

- Pregnancy
- Anaphylaxis or other severe hypersensitivity reaction

- Malignancy (with the exception of non-serious local and resectable basal or squamous cell carcinoma of the skin)
- Any serious infection or infection requiring treatment with an IV antimicrobial agent
- Any prohibited medication as defined in Section 4.3
- Any Grade 3 or greater thrombocytopenia (National Cancer Institute Common Terminology Criteria for Adverse Events [NCI CTCAE v4.0])
- Any Grade 4 neutropenia (NCI CTCAE v4.0)
- Failure to achieve a 20% improvement in both SJC and TJC (relative to baseline values in Study GA29350) at Week 24

Patients who discontinue study treatment prematurely for the reasons listed above will be asked to return to the clinic for an early termination visit (see Section 4.5.1) followed by 8 weeks of safety follow-up.

The primary reason for study treatment discontinuation should be documented on the appropriate eCRF. Patients who discontinue study treatment prematurely will not be replaced.

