Total Ig, IgG, IgM, IgA, and IgE concentrations will be measured regularly throughout the study. All patients in the study should be monitored for fever and potential infectious complications, including opportunistic infections and tuberculosis, and should be evaluated promptly. Physicians or a health care provider should give patients advice to prevent potential transmission of and exposure to endemic infections according to local or Centers for Disease Control and Prevention guidelines. Patients should be advised to seek immediate medical attention if they develop signs and symptoms suggestive of an infection. All infections occurring during the study, including but not limited to respiratory infections, cutaneous infections, urinary tract infections, systemic viral infections, and episodes of suspicious or febrile diarrhea, should be evaluated using serology or PCR if available and cultured if feasible and any identified organisms noted in the eCRF. Any serious infection, infection requiring IV antimicrobials (i.e., any Grade 3 infection) or any opportunistic infection is considered as an adverse event of special interest and should be reported to the Sponsor in an expedited manner as outlined in Section 5.2.3.

Guidelines for management of GDC-0853 in the event that infections are observed in patients are provided in Table 3.

Please also refer to the GDC-0853 Investigator's Brochure for further details.

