Appendix 1 Schedule of Assessments (cont.)

		Treatment Visits															
Week	0 ^a	4	8	12	16 ^b	20 ^b	24	28 ^b	32 ^b	36	40 b	44 ^b	48 ^b	52	SC/		
		28	56	84	112	140	168	196	224	252	280	308	336	365	SFU d		
Day (±days)	1 ^c	(±4)	(±4)	(± 4)	(±3)	(±3)	(±7)	(±7)	(±7)	(±7)	(± 7)	(±7)	(±7)	(±7)	(±7)	ET	UV ^e
PAXgene RNA blood	X ⁹ , x			X x										Х	x		
Optional blood sample for genotyping ^y	х																

ACR=American College of Rheumatology; CCP=cyclic citrullinated protein; CRP=C-reactive protein; DAS=DAS=Disease Activity Score; eCRF=Electronic Case Report Form; ESR= erythrocyte sedimentation rate; ET=early termination; HAQ-DI= Health Assessment Questionnaire—Disability Index; OLE=open-label extension; PD=pharmacodynamics; PK=pharmacokinetic; PPI=proton pump inhibitor; SC=study completion; SFU=safety follow-up; TBNK=T, B, and natural killer cells; UV=unscheduled visit; VAS=visual analog scale.

- ^a Day 1 OLE assessments that overlap with Day 84 assessments in the main Study GA29350 do not need to be repeated.
- ^b This clinical visit is required only for women of childbearing potential for their monthly urine pregnancy testing.
- ^c Day 1 of Study GA30067 should be Day 84 in the blinded Study GA29350.
- ^d Safety follow-up should occur 8 weeks (±7 days) after last dose.
- An unscheduled visit represents a visit that is not as per Schedule of Assessments and is required for an adverse event or for potential relapse assessment. All indicated assessments do NOT need to be performed at each unscheduled visit. Assessments should be based on the reason for the unscheduled visit. These assessments may include collection of PK and PD, to assess drug exposure and/or PD measures of drug activity. Assessments performed during unscheduled visits should be recorded on the corresponding eCRF(s).
- f Patients who wish to enroll in this OLE study must complete up to Day 84 of Study GA29350 (but should not take blinded study drug on Day 84) prior to signing OLE Informed Consent Form.
- ⁹ Day 84 assessments in Study GA29350 should be used as the Day 1 assessments of Study GA30067.
- h Includes pulse rate, systolic and diastolic blood pressures while the patient is in a seated position, and temperature.

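### Immunoglobulins are not scheduled at early termination or safety follow-up, nor SF-36v2 and FACIT-Fatigue at early termination; adding the marks is a cheap improvement

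*Combined protocol and SAP*

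**What the plan says.** **Visits for early leavers.** Section 4.5.1 states: "If a patient discontinues the study prior to the Week 52 treatment completion visit, an early termination visit should be conducted". It adds: "These patients should return for the 8-week safety follow-up visit in this study". Appendix 1 fixes the timing of that second visit: "Safety follow-up should occur 8 weeks (±7 days) after last dose". Section 4.5.2 sends patients with a mandatory treatment stop along the same path, ET and then follow-up.

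**Mandatory stops that matter here.** Section 4.5.2 lists "Any serious infection or infection requiring treatment with an IV antimicrobial agent", which can happen at any time, and "Failure to achieve a 20% improvement in both SJC and TJC (relative to baseline values in Study GA29350) at Week 24", which is tied to one scheduled visit.

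**Immunoglobulins.** Section 5.1.1.1, on infection risk, says: "Total Ig, IgG, IgM, IgA, and IgE concentrations will be measured regularly throughout the study". Appendix 1 marks the row "Quantitative Ig" at Weeks 0, 12, 24, 36 and 52 and at unscheduled visits. The SC/SFU and ET cells are empty. A footnote says that assessments at an unscheduled visit depend on the reason for it and need not all be done.

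**Questionnaires.** SF-36v2 and the "FACIT-Fatigue Scale" are secondary endpoints through or up to Week 52 (Section 2, Table 1). Appendix 1 marks both at Weeks 0, 12, 24, 52 and SC/SFU, with nothing at ET.

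**The concern.** The main issue is immunoglobulins. Section 1.3 reports lower IgG in high-dose dogs and rats and describes the immune effects in animals as reversible. Section 5.1.1.1 says it is unknown whether these effects carry over to humans, and it lists immunoglobulin measurement as part of infection monitoring. Table 1 includes laboratory changes both during and after dosing among the primary safety endpoints. Yet a patient whose infection forces a stop passes through two visits, ET and follow-up, and neither has an immunoglobulin sample on the schedule. Nor does anyone have one after the drug is withdrawn, so reversibility in humans is not observed systematically.

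The second issue is smaller. For a patient who stops between scheduled visits, the quality-of-life and fatigue record ends at the last scheduled visit and resumes only off drug. If such stops are related to how the patient feels, the on-treatment summaries lose the values nearest the decision to stop.

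**Working it through.** No stated figure in the plan bears on this point, so the check is a reading of Appendix 1 followed by simple subtraction.

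**Step 1. Marks by visit.** The table has 17 visit columns: 14 from Week 0 to Week 52, then SC/SFU, ET and unscheduled (UV). HAQ-DI and TBNK (T, B and NK cells) are included for comparison.

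| Row | Treatment weeks marked | SC/SFU | ET | UV |
|---|---|---|---|---|
| Quantitative Ig | 0, 12, 24, 36, 52 | no | no | yes |
| SF-36v2 | 0, 12, 24, 52 | yes | no | no |
| FACIT-Fatigue | 0, 12, 24, 52 | yes | no | no |
| TBNK | 0, 12, 24, 52 | yes | yes | yes |
| HAQ-DI | 0, 4, 8, 12, 24, 36, 52 | yes | yes | yes |

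The comparison rows show that ET is used for blood tests and for patient questionnaires, so the empty cells do not follow from what kind of visit it is.

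**Step 2. Oldest possible last value at a stop.** The age of the last scheduled value is at most the gap to the next scheduled one.

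- Immunoglobulins: gaps of 12 − 0 = 12, 24 − 12 = 12, 36 − 24 = 12 and 52 − 36 = 16 weeks. Maximum 16.
- SF-36v2 and FACIT-Fatigue: gaps of 12 − 0 = 12, 24 − 12 = 12 and 52 − 24 = 28 weeks. Maximum 28.

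The scheduled days agree: 365 − 252 = 113 days, or 16.1 weeks, and 365 − 168 = 197 days, or 28.1 weeks.

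**Step 3. A typical age, under an assumption.** The documents give no distribution of stopping times. If stops were spread evenly over 52 weeks, the mean age of the last value would be the sum of squared gaps divided by 2 × 52.

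- Immunoglobulins: (3 × 12² + 16²) / 104 = 688 / 104 = 6.6 weeks.
- Questionnaires: (2 × 12² + 28²) / 104 = 1072 / 104 = 10.3 weeks.

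So 16 and 28 weeks are worst cases. The even spread is only an illustration.

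**Step 4. Who is affected.**

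- *Stop before Week 12:* the only scheduled value of any of the three measures is Day 1, which is Day 84 of the parent study. For patients who came from placebo or adalimumab, that value precedes any GDC-0853.
- *Stop under the Week 24 joint-count rule:* all three measures are scheduled at Week 24, so the age is zero.
- *Stop for infection, or by patient or investigator decision, between visits:* the ages in Steps 2 and 3 apply.
- *Completers:* immunoglobulins at Week 52, none at follow-up.
- *Leaving during follow-up:* Section 4.5.1 asks for an ET visit, which has none of the three measures.

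**The case against.** A fair defence has several parts.

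- **Immunoglobulins exist before the event.** Every on-treatment infection has an earlier scheduled value at most about 16 weeks old. For risk, a value before the infection is the informative one; a sample taken afterwards cannot show which came first. An adverse-event visit may also include the test. This stands. A reader might infer that the study cannot relate immunoglobulin level to infection at all, and the documents do not support that. They support only that the value at stopping is left to discretion.
- **No contradiction in the text.** Roughly quarterly sampling is compatible with Section 5.1.1.1. A reader might see a conflict between that section and Appendix 1, but there is none, only a gap at two visits.
- **Lack of efficacy.** A reader might infer that data are lost selectively in patients stopped for lack of efficacy. For the protocol-defined rule this is wrong, since all three measures are scheduled at the visit where it is applied. The gap concerns stops at other times.
- **Early leavers still give data.** ET collects every ACR component, and follow-up collects both questionnaires. Asking the longer questionnaires less often is a normal choice about burden. This stands, but the follow-up value is 8 weeks off drug and does not describe the patient at stopping.
- **ET may itself be off drug.** Section 4.5.2 sets no interval between last dose and ET. This is also true, so an ET value should be called a value at stopping, not necessarily one on treatment.

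None of this supplies an immunoglobulin value after the drug is withdrawn. Appendix 1 schedules TBNK at both ET and follow-up, and the documents give no reason for treating immunoglobulins differently.

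**Conclusion.** The point holds as a low-cost improvement, not as a flaw that threatens the main conclusions.

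- **Immunoglobulins, the stronger part.** There is no scheduled value at an infection-driven stop; the fallback is one up to about 16 weeks old or a discretionary sample. No patient has a scheduled off-drug value.
- **SF-36v2 and FACIT-Fatigue, the lesser part.** There is no value at stopping for patients who leave between scheduled visits. The last on-treatment value is up to 28 weeks old, and the next is 8 weeks off drug.

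A reader might go on to infer that the secondary endpoints are materially biased, or that ET questionnaires would repair them. Neither follows. The documents give no discontinuation rates, so no bias can be sized, and several mandatory stops, such as pregnancy or malignancy, are not defined by quality of life or fatigue. An ET value also does not stand in for a missing Week 52 value. Section 6 gives no missing-data rule and leaves analysis details to a Data Analysis Plan.

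The conclusion rests on the empty Appendix 1 cells being intended as empty, and on early leavers attending the ET and follow-up visits.

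**What to change.** In Appendix 1:

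1. Mark quantitative immunoglobulins at ET and at SC/SFU.
2. Mark SF-36v2 and FACIT-Fatigue at ET.

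No new visit is needed. ET already includes blood for CRP, TBNK, lipids and PK, together with the HAQ-DI and the patient VAS scales. SC/SFU already includes hematology, chemistry, CRP and TBNK. The cost is a small assay charge per patient at each of the two visits, and two short questionnaires at ET (36 + 13 = 49 items).

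Two related matters can be settled at the same time. The Data Analysis Plan should say how ET values are used and how a missing Week 52 value is handled, since the new marks do not answer that. The sponsor should also check whether the empty ET cells for hematology and chemistry are intended.
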